Subjects will be recruited from among patients at a Prisma Health-Upstate Emergency Department (ED) at either Greenville Memorial Hospital, Greer Memorial Hospital or Baptist Easley Hospital if testing for a SARS-CoV-2 infection is performed and the potential subject will be discharged to home from the ED. Potential subjects who express a desire to be evaluated for possible enrollment on trial will have their chart screened by one of the ED Investigators to ensure they meet all inclusion criteria without any exclusion criteria. If they have not had an eGFR measured within a year of enrollment, a blood draw will be performed to measure their eGFR. Female participants who are of childbearing potential, i.e., 15 to 55 years old and have not had their uterus surgically removed (i.e., hysterectomy) or both ovaries removed surgically, will have a urine pregnancy test performed. A pregnancy test will

not be performed if they would otherwise fit the category of childbearing potential described above but are of a confirmed postmenopausal state. After enrollment and while still in the ED subjects will have a blood draw for research labs that will be collected into two tubes. One tube will be sent to the main lab where it will be held. If the subject tests positive for a SARS-CoV-2 infection, they will be randomized within 24 hours of a positive test. A CURB-65 Assessment Form will be completed by the ED Investigator research staff member and a CAP-SYM 18 survey will be administered the ED Investigator. For male subjects an IPSS survey will also be completed by the ED Investigator. All subjects who have been enrolled will be provided with a signed copy of their Informed Consent Form, a copy of their signed Research HIPPA Authorization form, 30 copies of the daily diary CRF, 4 copies of the medication log CRF, an instruction sheet for the Roth Score and 40 Step Test and 4 sterile urine specimen containers.

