The randomization process will be performed using the Randomization module within REDCAP®. This will be performed through use of the data entry form entitled, “COVID-19 Test Result and Drug Randomization Case Report Form.” If the subject has a Rapid Test Performed in the ED and a positive result is obtained prior to discharge, the Co-Investigator who enrolled the subject will be able to access this form and perform the randomization. Otherwise, the randomization will be performed by the PI. Due to the trial design as a Phase I trial, the number of subjects on any arm can vary from zero to six depending on any dose limiting toxicities that may occur. Also, a new zone in the trial will not be able to open until all subjects in the previous zone have completed the trial. Therefore, the randomization process will be dynamic which REDCap® is incapable of handling directly but is capable of handling indirectly in a two-step process as described below. Prior to the start up the trial, a randomization lookup table will be uploaded into REDCap®, which will be nothing more than an ordered table from one to one hundred. While this may seem trivial, it is utterly essential in order to harness the power of REDCap® for a dynamic randomization process. After an investigator has performed the randomization task in REDCap®, the randomization number will be returned from this table. The investigator will then be required to lookup manually the arm to which the subject has been randomized in a file called “Dynamic Randomization Lookup Table” which they will only find within the “File Repository” in REDCap®. An example of this file can be found in the Appendix below. This file will be created prior to the trial initiation by the Lead Statistical Investigator initially assuming three subjects for each trial arm. Anytime, a change is needed to the “Dynamic Randomization Lookup Table” due to a DLT, the PI will suspend the ability for anyone to enroll or randomize a subject through the “User Rights” feature of REDCap® which can be used to restrict access by role to data entry forms. Once a decision has been made about either expanding or closing a trial arm due to a

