DLT based on the trial rules and assuming the IRB and DSMB which will have also been notified of the DLT, have not imposed further restrictions, the PI will obtain from the Statistical Lead Investigator a new “Dynamic Randomization Lookup Table.” The old “Dynamic Randomization Lookup Table” will be removed from the REDCap® “File Repository” but an electronic copy will otherwise be maintained by the Lead Statistical Investigator. The new “Dynamic Randomization Lookup Table” will be uploaded into the file repository and the User Rights to the enrollment and randomization data entry forms in REDCap® will be restored.

After the investigator has determined the trial arm to which the subject has been randomized through the two-step process as described above, the investigator will verify that they correctly accessed the “Dynamic Randomization Lookup Table” in the form entitled, “COVID-19 Test Result and Drug Randomization Case Report Form.” The remainder of the form will be completed to include entry of the trial arm and verification that the correct prescription has been entered. The subject will be notified of the randomization and prescription entry. Whenever, a Randomization CRF is saved, the PI will receive an immediate electronic notification via REDCap® and the PI will then complete the Investigator Assignment Form in REDCap®, a copy of which can be found in the Appendix. It is through this form that the subject will be assigned to an individual Investigator and an individual Research Assistant for the remainder of their trial participation. The assigned Investigator and Research Assistant will be immediately notified electronically via REDCap®. The subject will be notified by the PI to which Investigator and Research Assistant they have been assigned. Unless the subject has declined a Vivify® electronic device, such device, the trial medication and paper copies of the medication log and daily diaries will be delivered to the subject’s home within 24 hours of randomization by a courier who will have the appropriate training and PPE. If the subject has declined a Vivify® electronic device, they will be required to pick-up their study drugs and paper copies of their forms at an Upstate Pharmacy.

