After a subject has been randomized to a combination of trial drugs the Prisma-Health lab will be notified to process the first tube of blood for a determination of the subject’s blood type and Rh factor. The second tube will be sent to Kiyatec® to determine their Glutathione level, a cytokine panel (IL-1 β , IL-2, IL-6, IL-8, IL-10, IFN γ , TNF α and GM-CSF), and their tryptase level. The collected urine sample will also then be sent to Kiyatec® to measure the subject’s F2-Isoprostane level, creatinine level, a cytokine panel (IL-1 β , IL-2, IL-6, IL-8, IL-10, IFN γ , TNF α and GM-CSF), n-methylhistamine level and TMRSS2 levels. The research labs will be held, and the tests will only be performed if the subject is randomized to take an investigational

drug. Otherwise the specimens will be discarded. The lab evaluations to be performed by Kiyatec® will be kept frozen and typically run in batches of 40.

If the SARS-CoV-2 test results are negative after enrollment, the subject's participation in the trial will be completed and randomization to an investigational drug will not occur. An alert will be triggered within REDCap® with an immediate electronic notification to the PI both when a subject has been enrolled and when they have been randomized. When a zone has completed accrual, a text message will be sent by the PI to all investigators that the trial is temporarily closed to accrual, and the enrollment and randomization forms in REDCap® will be taken offline. When all subjects within the current zone have completed the trial, and the trial is not closed due to toxicity, the next zone will be opened. All Investigators will be notified by text message from the PI when a new zone is open and the enrollment and randomization forms in REDCap® will be placed back online.

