Within 3 days of a positive SARS-CoV-2 test for an enrolled subject, a research assistant will complete the Baseline Data form in REDCap®. The CBC, BMP, Coag, Crp, Liver Panel, Pregnancy Test, EKG, Blood Gas and PSA Forms will also be completed in REDCap® if any of the corresponding studies were completed within a year prior to enrollment and if so only the most recent value will be recorded. A Starting Medication Form will also be completed in REDCap® for every medication the subject is taking at the time of randomization. These Forms can all be found in the Appendix.

c. Randomization Data Collection Process

Within 1 day of a positive SARS-CoV-2 test, a subject previously enrolled will be randomized to combination of drugs by completing the COVID-19 Test Result and Drug Randomization Case Report Form in REDCap®. If the result is known before discharge from the ED this form will be completed by the Investigator in the ED and the PI will be immediately sent an email via a REDCap® alert which will indicate the Subject’s study identification number and dose combination to which they were randomized. If the SARS-CoV-2 test result is returned after discharge home from the hospital, this form will be completed by the PI. This form also contains a checklist to document, the date of the positive result, that the prescription was sent to an Upstate Pharmacy, that the subject was contacted to pickup the prescription, that the subject was reminded to complete the medication log and daily diary forms. Within 24 hours of randomization, the PI will assign the subject to a non-ER study investigator and research assistant. The PI will notify the subject, investigator and research assistant of these assignments and document such in REDCap® using the Investigator Assignment Form.

d. Research Lab Data Collection Process

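### If randomization numbers are issued in table order, the readable lookup file lets the PI know the next arm in any zone with two or more open dose arms

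*Combined protocol and SAP*

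**What the plan says.** All references are to the combined protocol and SAP.

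- **Number.** Section III.ii describes a two-step process. REDCap returns a number from a table "which will be nothing more than an ordered table from one to one hundred".
- **Arm.** Next, "The investigator will then be required to lookup manually the arm to which the subject has been randomized in a file" kept in the REDCap File Repository. "This file will be created prior to the trial initiation by the Lead Statistical Investigator initially assuming three subjects for each trial arm". It is replaced when a DLT changes an arm.
- **Who randomizes.** If a rapid test is positive before ED discharge, the co-investigator who enrolled the subject randomizes. "Otherwise, the randomization will be performed by the PI".
- **What the PI is told.** "Whenever, a Randomization CRF is saved, the PI will receive an immediate electronic notification via" REDCap. The same section repeats that there is an "immediate electronic notification to the PI both when a subject has been enrolled and when they have been randomized". Section III.iv.c adds that, after an ED randomization, the PI is emailed the "study identification number and dose combination to which they were randomized".
- **Time window.** For subjects who test positive, "they will be randomized within 24 hours of a positive test".
- **Allocation.** Section III.i (Phase I Portion) uses block randomization among the open combinations of a zone. No block size is given.

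The only access control described for randomization is suspension of the enrollment and randomization forms while the lookup file is changed or a zone is closed. The text read for this review contains no step that hides unused rows or releases one assignment at a time.

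**The concern.** Block randomization within a zone lets chance decide which subject receives which open combination. That protection fails if the person randomizing can see the next assignment. Here the key is open to the randomizer by design, and an ordered list of numbers appears to give away the position in it.

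Nobody has to break a rule for this to matter. The PI handles every subject whose positive result arrives after ED discharge. With two such subjects waiting inside the 24-hour window, taking one before the other settles who gets which arm.

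Arms start with three subjects, and under section III.i one DLT in three sends an arm to expansion. A DLT is any toxicity of grade 3 or higher, with no explicit attribution requirement. Section V.ii counts adverse events whatever their cause, including the infection itself. So the arm that receives a sicker subject may show a DLT that reflects the subject and not the combination.

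**Working it through.** The plan states no figure on this point, so there is none to reproduce.

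**Inputs.** From the documents: three subjects per arm initially (III.ii) and a DLT rate of 5-8% (IV.ii). Assumed: two or three open arms, because Figure 10 is not shown; one large block or the smallest possible blocks, because block size is not stated; and numbers issued in table order, which is the natural reading of III.ii but is not said outright.

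**1. How predictable is the next arm?** With the file and the last number: 100%. With the order hidden but past assignments known, the best strategy is to guess the arm with most slots left in the block. Let E be the expected number of correct guesses. At each step E = (largest remaining count)/(total remaining) + the average of E over the possible next states.

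| Open arms | Blocks | Expected correct | Share |
|---|---|---|---|
| 2 | one of 6 | 4.1 of 6 | 68% |
| 2 | three of 2 | 4.5 of 6 | 75% |
| 3 | one of 9 | 4.79 of 9 | 53% |
| 3 | three of 3 | 5.5 of 9 | 61% |

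**2. If two positives are pending, does their order matter?** It does when the next two slots are different arms. Averaged over adjacent pairs:
- two arms, one block: 3/5 = 0.60
- two arms, blocks of 2: (3×1 + 2×1/2)/5 = 0.80
- three arms, one block: 6/8 = 0.75
- three arms, blocks of 3: (6×1 + 2×2/3)/8 = 0.92

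These figures are conditional on two positives being pending together. The documents give no accrual rate, so the frequency of that event is unknown.

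**3. What could one steered subject do to an arm's DLT count?** This is an illustration only. Let p be the usual DLT risk and r the risk of a sicker subject, assumed 20%.
- Arm without that subject, 1 − (1−p)³: 0.143 at p = 0.05; 0.221 at p = 0.08.
- Arm with that subject, 1 − (1−p)²(1−r): 0.278 at p = 0.05; 0.323 at p = 0.08.

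Under concealed allocation the sicker subject still enters some arm of the zone. The right comparator is therefore random placement among k arms, [(k−1) × without + with]/k:
- two arms: (0.143 + 0.278)/2 = 0.210; (0.221 + 0.323)/2 = 0.272
- three arms: (2×0.143 + 0.278)/3 = 0.188; (2×0.221 + 0.323)/3 = 0.255

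The excess from steering equals (1 − 1/k)(1−p)²(r−p):
- two arms: ½ × 0.9025 × 0.15 = 0.068 at p = 0.05; ½ × 0.8464 × 0.12 = 0.051 at p = 0.08
- three arms: ⅔ × 0.9025 × 0.15 = 0.090 at p = 0.05; ⅔ × 0.8464 × 0.12 = 0.068 at p = 0.08

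The same formula with r = 10% gives about 1-2 points (two arms) or 1-3 (three arms). With r = 30% it gives about 9-11 or 12-15.

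**The case against.** **Missing Appendix items.** The example lookup file (cited in III.ii) and the figure of access rights by role (cited in VI.ii) were not in the text read, and might show a restriction. This lowers certainty about what else is hidden. It cannot remove the access that III.ii itself requires of whoever randomizes.

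**Not every randomizer can predict.** A reader might infer that all randomizing investigators can foresee the next arm. The documents do not support that. Only the PI is documented as receiving the alerts, and nothing tells an ED co-investigator at one of three hospitals the last number used. Enrollment also precedes the result for non-rapid tests, so the assignment cannot be foreseen with certainty at enrollment. The PI's own foresight fails if an ED randomization comes in between. This objection stands, and it confines the point to the PI and to anyone else who learns the last number.

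**Size of the DLT effect.** A reader might compare 28-32% with 14-22% and infer a shift of 10-14 points. That comparison treats the sicker subject as absent from the zone under concealment, which is wrong. The excess is about half to two thirds of that.

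**Limited purpose of the blocking.** Section III.i gives its aim as controlling the number per dose, the escalation rules work arm by arm, and III.v describes descriptive statistics. This also stands, and it limits what is at stake. Concealment still matters, because an arm's DLT count decides its path and depends on who was placed there.

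**Conclusion.** The point holds in limited form. In a zone with two or more open arms, and assuming issue in table order, the ordered table and the readable lookup file make the next arm certain to anyone who knows the last number used. The PI is documented to be that person.

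The consequence is confined to which subjects fill each arm within a zone, and so to arm-level DLT counts. Zone 1, stages with a single open arm, and the 3+3 counting rules are unaffected. The frequency of reordering, and the bias it would cause, cannot be derived. The 5-7 and 7-9 point figures describe one steered subject at an assumed 20% risk and do not estimate what would happen in the trial. Nothing in the documents suggests that anyone intends to steer subjects. The point is best treated as a cheap improvement.

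**What to change.** Before the start, the statistician uploads a randomly permuted 1-100 table in place of the ordered one. Viewing of the uploaded table is restricted to the statistician. The restriction must also cover the PI, who otherwise operates User Rights in REDCap. Each Dynamic Randomization Lookup Table, including those reissued after a DLT, is built against that hidden order. This keeps the two-step process and immediate ED randomization. The cost is one restricted right, a sentence in III.ii and slightly more work for the statistician.

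If the PI's view cannot be restricted, the statistician or pharmacy should hold the lookup file and release only the current subject's arm after REDCap has issued the number. That needs a reachable person and may add a short delay within the 24 hours already allowed.

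Either way some predictability remains, because filled slots can still be counted. The change would therefore recover only part of the excess illustrated above.

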The main risks to Famotidine which have been occurred in greater than or equal to 1% of subjects in clinical trials are: headache; dizziness; and constipation.

Other adverse reactions that were reported in less than 1 % of subjects in clinical trials include: fever, abnormal weakness or lack of energy; fatigue; heart palpitations; elevated liver enzymes; vomiting; nausea; abdominal discomfort; decreased appetite; dry mouth; decreased platelet counts in your blood; swelling of the tissue around your eyes; rash; eye redness and irritation; difficulty breathing; muscle pain; joint pain; seizure; hallucinations; depression; anxiety; decreased interest in sexual intercourse; difficulty falling asleep; prolonged sleeping; dry skin; flushing; ringing in your ears; altered sense of taste; and difficulty in men with achieving erections capable of intercourse. The following have also been reported during post-approval use of famotidine: changes to your heart by effecting the rhythm in which it beats; jaundice; inflammation and possible damage to your liver; decreased levels of white blood cells, red blood cells or platelets which could be life threatening; allergic reaction which could be life-threatening; rapid swelling of soft tissues often involving tissue around the face, limbs or genitals; hives; muscle damage; muscle cramps; confusion; agitation; tingling, numbness, or burning sensation in the skin often involving hands, feet, arms, or legs; pneumonia; and rash and blistering which could be life threatening.

In a recent prospective trial of patients with Parkinson's disease, doses of famotidine were escalated from 80 mg/day to 120 mg/day to 160 mg/day. No significant adverse effects were observed.¹⁵¹

11. Possible Reduction in Absorption of NAC due to increased Gastric pH

It is conceivable that due to the reduction in gastric pH that oral NAC may not be absorbed as effectively when given in combination. In order to mitigate this theoretical possibility, we have proposed a phase I trial of the combination of the two investigational drugs with twelve possible combinations described in greater detail below. Three arms are with NAC alone. Additionally, while the trial design should allow us to evaluate the possibility of a decreased effectiveness of NAC in combination with FAM, we make the following observations to conclude that it is unlikely that the increased gastric pH will decrease the absorption of NAC.

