It has been demonstrated that if NAC is absorbed in its protonated form, NACH_2 , this would have to occur in the stomach because very little NAC exists in this form at a pH greater than 4.0.¹⁵² Thus, if NAC is only absorbed in the stomach then the combination with FAM could virtually negate any effect of NAC as very little might be absorbed. However, it was demonstrated in a study of radiolabeled NAC delivered orally to rats that NAC was incorporated into the intestinal and liver glutathione stores as early as 30 minutes after ingestion.¹⁵³ Therefore, since NAC exists predominately in its monoanionic form, NACH^- , in a pH range from 4 to 9,¹⁵² this study¹⁵³ would suggest that NAC can be absorbed effectively within the intestines and would likely be transported by some form of an anionic transporter, with the Organic Anion Transporting Polypeptide (OATP) B-21 a

potential candidate. If a significant amounts of NAC are transported in the intestines as it appears, then raising the gastric pH may have little effect since oral NAC is ingested in its functional form and doesn't depend on digestion by gastric enzymes that might be less efficient at a higher gastric pH.

12. Possible Synergistic Effect between FAM and NAC via enhancement of Lymphocytes and IL-2 Production

Famotidine use in a retrospective non-peer-reviewed report has observed to be associated with a significantly lower risk of death or intubation (10% versus 22%, $p < 0.01$) if it was given in the first 24 hours of a patient's admission to the hospital for a SARS-CoV-2 infection.¹⁵⁴ In this report the dose of famotidine was relatively low as famotidine users received a median of 5.8 days of drug for a total median dose of 136 mg (63 to 233 mg).

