Given the existing biochemical data to suggest FAM inhibits suppression of intraepithelial lymphocytes by histamine and Mast Cell release of histamine; the correlation of severity of tissue fibrosis and thrombosis with ACE2 depletion; the ability of NAC to reduce oxidative stress, which appears related to severity of the SARS-CoV-2 infection; the ability of NAC to prevent tissue fibrosis, thrombosis and reduce viral replication; the favorable side effect profiles of FAM and NAC; the wide prevalence of SARS-CoV-2 infection and its substantial mortality rate; and, the lack of vaccine or proven therapies for non-hospitalized patients who have tested positive for a SARS-CoV-2 infection; a clinical trial of the safety and efficacy of the combination of NAC and FAM is justified. These medications are readily available and their combination does have the possibility of reducing the severity of infection and mortality for these patients (see figure 9).¹⁷⁰

[figure not shown]

Figure 9: A cartoon drawing¹⁷⁰ of the putative effect of FAM to reduce inhibition of Intra-Epithelial Lymphocytes and of NAC to reduce severity of infection through reduction of oxidative stress and reduction of viral replication

III) RESEARCH DESIGN AND METHODS (including data analysis)

i) Study Design - Parallel Phase I/II Clinical Trial

The proposed parallel phase I/II design allows for simultaneously evaluating the safety and efficacy of combination dose levels and to select the optimal combination dose. The trial is started with an initial period of dose escalation, and then patients are randomly assigned to permissible dose levels. Bayesian posterior probabilities are used in the randomization to adaptively assign more patients to doses with higher efficacy levels. Combination doses with lower efficacy are temporarily closed and those with intolerable toxicity are eliminated. The trial is stopped if the posterior probability for safety, efficacy or futility crosses our pre-specified boundaries. This design has been shown in simulations to save sample size, to have better power and efficiently assigns more patients to doses with higher efficacy levels.¹⁷¹

Phase I Portion (Dose Escalation Phase)

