The doses to be tested for famotidine are 20 mg thrice daily, 40 mg thrice daily, 80 mg thrice daily and no famotidine. The doses to be tested for n-acetyl cysteine are 600 mg thrice daily, 1200 mg thrice daily and 1800 mg thrice daily. The dose combinations are labelled 1 through 12 and are zoned as illustrated in Figure 10. The first zone has the combination of the lowest dose of each drug. The second zone has the combination of the lowest dose of each drug with the middle dose of each drug. The dose escalation starts with the first zone and follows with the second zone and then each combination of doses in the zone next closest to the coordinate

[figure not shown]

Figure 10. Dose Combinations of N-Acetyl Cysteine and Famotidine

origin shown in figure 10. Combination doses in the same zone are tested simultaneously using block randomization to control the number of patients for each open dose. Some combinations doses may close, in which case blocked randomization is applied to the remaining open combination doses in the same zone. A modified “3+3” design¹⁷² will be used for the initial dose escalation.

To find acceptable dose levels any grade 3 or higher toxicity will be considered a dose-limiting toxicity (DLT). The modified “3+3” design proceeds as described below. Three patients receive dose level 1. Their responses determine the subsequent steps as described in the following decision rules.

- (1) If two patients (2/3) experience DLT, then we close dose level 1 and all larger doses to testing.
- (2) If no patient experiences DLT, then we designate dose level 1 as an admissible dose, and open doses in zone 2 for testing.
- (3) If only one of the first three patients (1/3) experiences DLT, then we assign three more patients to dose level 1. In this case, we assign up to six patients to this dose, and the following decision rules apply:
 - a. If only one of the six patients (1/6) experiences DLT, then we designate dose level 1 as an admissible dose, and open doses in zone 2 for testing.
 - b. If two of the six patients (2/6) experience DLT, then we designate dose level 1 as an admissible dose, and doses in zone 2 and higher are closed to testing.
 - c. If more than two of the six patients (>2/6) experience DLT, then we close dose level 1 to testing, and we also close doses in zone 2 and higher.

ii) Study Procedure

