Responsibilities and those tasks and responsibilities delegated to co-investigators and all others participating in the conduct of this trial are specified in the Appendix in the Table with the heading, "Responsibilities and Delegated Tasks and Responsibilities"

iii) Inclusion / Exclusion Criteria

Inclusion criteria:

- (1) Age > 18**
- (2) performance of a SARS-CoV-2 test within 1 day of enrollment**

Exclusion criteria:

- (1) All patients under 18**
- (2) Known allergy to N-Acetyl Cysteine**
- (3) Known allergy to famotidine or other H₂-receptor antagonists**
- (4) Pregnant or Nursing Mothers**
- (5) Laboratory Evidence or History of Renal Impairment (eGFR < 30 mL/min/1.73 m²)**
- (6) Taking H₂-receptor antagonists, hydroxychloroquine or chloroquine.**
- (7) Patient has been admitted to the hospital prior to study enrollment**

iv) Data Collection Methods

Please note that for ease of reference a figure is included in the Appendix of the mapping of the Data Collection Instruments to be used in REDCap[®] with the corresponding events as described in outline form below.

a. Enrollment Data Collection Process

Data will be collected in the ED by a study Investigator by taking a patient history, performing a physical exam and performing a chart review to ensure all inclusion criteria are met and that no exclusion criteria exist. The Investigator will complete the Eligibility Assessment CRF, Demographics CRF, IPSS Questionnaire, CAP-SYM 18 CRF and the Post Enrollment Checklist directly into REDCap[®]. Adobe Acrobat pdf copies of these forms are included in the Appendix. It should be noted that these forms include branching logic that will indicate the subject is not eligible for enrollment if they do not meet the eligibility criteria, have any excluded conditions or have not had a pregnancy test if

required. Additionally, the Post Enrollment Checklist has branching logic to ensure that the subject has meet all eligibility criteria without any exclusion criteria being met and that all the forms mentioned above have been saved and marked with a status of “Complete.” After the Post Enrollment Checklist has been marked complete, the PI will immediately be sent an email via a REDCap® alert which will indicate the Subject’s study identification number and the name of the enrolling Investigator.

b. Post-Enrollment Data Collection Process

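### Criterion 6 bars background H2 blockers but not current use of N-acetyl cysteine, the drug given in every arm, so a subject can receive more NAC than the level at which toxicity is counted

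*Combined protocol and SAP*

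**What the plan says.** The exclusion list (section III, Inclusion / Exclusion Criteria) has seven items. Only item 6 concerns drugs the patient is already taking: "Taking H₂-receptor antagonists, hydroxychloroquine or chloroquine". NAC is named once, as "Known allergy to N-Acetyl Cysteine". The text available has no washout rule and no list of prohibited medication.

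Every arm contains NAC. Section III.i states: "The doses to be tested for n-acetyl cysteine are 600 mg thrice daily, 1200 mg thrice daily and 1800 mg thrice daily". These are crossed with three famotidine doses or none. A toxicity of grade 3 or higher is a DLT, and the count at a level decides whether it is expanded, admitted or closed.

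Medication use is recorded, not restricted. The Starting Medications form is completed after enrollment and lists what the subject takes at randomization. The New Medications form covers later changes made by an investigator or another provider and documented in the electronic record. Data Analysis Methods mentions descriptive statistics and gives no use for either form.

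On gastric pH, section II.i.b.11 says: "It is conceivable that due to the reduction in gastric pH that oral NAC may not be absorbed as effectively when given in combination". It adds "Three arms are with NAC alone" and that "the trial design should allow us to evaluate the possibility of a decreased effectiveness of NAC in combination with FAM". It also states that "if NAC is only absorbed in the stomach then the combination with FAM could virtually negate any effect of NAC", then argues that reduced absorption is unlikely.

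**The concern.** The list protects one trial drug from background use and leaves the other open, without giving a reason. The open one is the drug every subject receives. A patient who arrives already taking NAC meets all the criteria, is given trial NAC on top, and is counted at the assigned level.

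Two things are at stake. The first is dose attribution: the escalation decisions rest on three to six subjects per level, so one subject whose intake differs from the label carries weight. The second is Aim 2. The protocol cites a placebo-controlled human trial in which oral NAC 600 mg twice daily lowered IL-6 and IL-1 (section II.i.a.7), and a study in which 600 mg by mouth raised glutathione in lavage fluid (section II.i.b.6). On that evidence, prior NAC could move the baseline of markers the trial wants to interpret.

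A lesser matter concerns the NAC-alone arms. They are offered as the reference without acid suppression, yet only H2 blockers are kept out of them.

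**Working it through.** The plan states no figure on this point to reproduce. The check reads the criteria against the dose grid and decision rules, then sizes the effect under stated assumptions.

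**Dose received.** Assigned daily NAC is 600 × 3 = 1800, 1200 × 3 = 3600 and 1800 × 3 = 5400 mg. Received = assigned + background. The background is an assumption. 1200 mg/day is the 600 mg twice-daily regimen of an influenza trial the protocol cites; 1800 mg/day is one step of the grid.

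| Assigned (mg/day) | With 1200 background | With 1800 background |
|---|---|---|
| 1800 | 3000 (+67%) | 3600 (+100%) |
| 3600 | 4800 (+33%) | 5400 (+50%) |
| 5400 | 6600 (+22%) | 7200 (+33%) |

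The smaller assumption is 1200/1800, two thirds of a step. Under the larger one, a subject at either lower level receives exactly the next level's total. For context, the NAC side-effect section cites a trial with a maximum tolerated dose of 1800 mg twice a day, which is 3600 mg/day. The middle level equals that total and the top level exceeds it before any background intake.

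**Decision rules.** The rules are written for dose level 1; I take them to apply to later levels. Suppose one DLT occurs in a subject with background NAC:

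- No other DLT: 1/3 brings in three more subjects. A final 1/6 is admissible and escalation continues.
- One other DLT: 2/3 closes the level and all larger doses. If the count is instead 2/6, the level stays admissible but higher zones close.
- Two other DLTs among six: 3/6 closes the level and the higher zones.

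Alone, the subject can only expand the level. With one or two other DLTs, the subject can be the one who tips the decision.

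**How many subjects.** The documents give no prevalence. Take p = 1%, 2% or 5% as an assumed range, with the planned 42 subjects. The expected number of NAC users, 42p, is 0.42, 0.84 or 2.1. The chance of at least one, 1 − (1 − p)^42, is 34%, 57% or 88%.

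**Other acid suppressants in the NAC-alone arms.** Three arms of three give 9 subjects, if all three arms open and none expands. With assumed use of 5%, 10% or 20%, the chance of at least one user, 1 − (1 − p)^9, is 37%, 61% or 87%. That probability is not the loss of information. If another acid suppressant affected NAC absorption as famotidine might, and added nothing in the famotidine arms, the expected contrast would shrink by the factor 1 − p. Expected users are 9p = 0.45, 0.9 or 1.8, and 95%, 90% or 80% of the contrast remains.

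**The case against.** The strongest reply is that nothing shows this happens often. The remark "These medications are readily available" belongs to the trial rationale and is not evidence of use among emergency patients. The 1200 mg/day figure is a trial regimen, not an observed background intake. Nor is extra toxicity shown: in the cited influenza trial, adverse events on 600 mg twice daily (9%) did not differ significantly from placebo (5%). All of this stands, though that trial tested the dose alone and not on top of 1800 to 5400 mg/day. The toxicity risk is therefore unquantified, not excluded.

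A second reply is that the data are already there. The Starting Medications form would identify users afterwards, and the first glutathione sample is taken in the emergency department before study drug. This stands in part. The form screens no one, on-study capture depends on a provider's entry in the record, and no analysis is said to use either. The early sample measures a shifted baseline but does not explain it.

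Two stronger readings are tempting. A reader might infer that one DLT in a NAC user can close an arm; the rules above do not allow that without further DLTs. A reader might also infer that the NAC-alone arms fail as a reference. The documents do not support that. The comparison is informal, no test is specified, the protocol judges a pH effect unlikely, and the assumed range gives modest dilution.

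The Eligibility Assessment CRF is not reproduced, so a question on NAC use there cannot be ruled out. The protocol describes its logic as enforcing the listed criteria.

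**Conclusion.** The point holds for current NAC use. As written, the criteria admit a subject whose total NAC intake exceeds the assigned level, and the escalation rules count that subject at the assigned level. For each affected subject the discrepancy is +22% to +67% under an assumed 1200 mg/day background. How many subjects are affected is unknown, because the documents give no frequency. The effect on escalation is expansion of a level by itself, and closure of a level or a stop to escalation only in company with other DLTs. The point is worth acting on because the correction is nearly free and the cohorts are very small.

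For other acid suppressants the point is weaker. There the dose taken is as assigned and only absorption might differ. This supports a sensitivity analysis and not an exclusion.

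**What to change.** Add current use of NAC from any source to criterion 6, and add the matching question to the branching logic of the Eligibility Assessment CRF. The cost is one phrase, one form item and a few NAC users who become ineligible.

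Secondarily, use the Starting Medications data to flag subjects taking acid suppressants other than H2 blockers. Report the NAC-alone versus NAC-plus-famotidine comparison both with and without flagged subjects. This needs no new data and excludes no one from the trial; the restricted version is slightly smaller.
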